9.1. Informed consent

Participating patients will need to provide written consent either on paper or online format. To do this they will complete the study consent form for their part - Study Consent Form Part 1. Please see section 7.1 for more information around consent.

For part 1, consent form B is optional, and provides an opportunity for participants to provide their contact details, should they wish to be informed of any future relevant research projects from our team. This is not a requirement for completion of this

research. It is stressed that completing this is entirely optional, and participants should not complete this page if they do not want to be contacted about future research. Completing this section does not commit the participants to be involved in future research. Any future research would need separate ethical approval.

9.2. Screening and recruitment

Screening and recruitment has been previously described in detail. Please see section 7.1 for more information.

9.3. Study interventions

Questionnaire 1:

Eligible participants determined by the inclusion criteria will be asked to complete a specially developed questionnaire regarding their socio-demographics, personal and family medical history, HRQoL and cancer worries.

Assessment	Part 1 Quest	: tionnai	Part 2A: Development of Questionnaire 2		it of re 2	Part 3A: Development of Questionnaire 3			
Eligibility confirmation	X								
Consent		Х							
Complete questionnaire			Х						
Interviews with patient representatives				Х			Х		
Interviews with clinical experts					X			Х	
Piloting of questionnaire						Х			Х

9.4. Schedule of Assessment

9.5. Study Flowchart

Note – the short online screening questionnaire is only for participants completing the study online. Participants who are sent a paper study and choose to complete this on paper do not have to complete this screening questionnaire, as they will have been screened by their treating clinician.

9.6. Data collection

A secure customised database will be created for the study, held securely at Queen Mary University of London. Electronic versions of questionnaires will be held on secure servers at Queen Mary University of London. Data entered into this electronic questionnaire will be held on this secure customised database. An electronic case report form (eCRF) will be used for each study participant.

Completed paper consent forms and questionnaires will be returned via a freepost self-addressed envelope to the PRESCORES research team at Queen Mary University of London. The PRESCORES research team will retain optional consent form B and the questionnaire, and post consent form 1 to sites. Completed paper consent form 1 will be securely stored at participating sites. Completed paper questionnaires and optional consent form B will be securely stored at Queen Mary University of London.

Consent forms will be stored at site, separately from identification logs. Researchers at QMUL will enter data from paper documentation onto eCRFs on the customised electronic database. Support from a data capture company/service may be used if required. These data are pseudo anonymised.

No data will be collected by any other sites. All source data will be handled, computerised and stored in accordance with QMUL Information Governance guidelines, GDPR and GCP. Please see section 13 for further information on data handling.

9.7. Follow-up Procedures

There will be no follow-up for any participant in any part of the study. Upon completion of the relevant questionnaire (and return of the consent form and questionnaire for those completing on paper), there will be no further involvement in the study.

9.8. Participant withdrawal

Volunteers are free to withdraw from the study at any time, through personal choice or without giving any reason for doing so. Information on how to do this is provided in each PIS, and on the consent forms. The co-ordinating centre team will be informed of all withdrawals.

9.9. End of Study Definition

The end of study is defined as 36 months after receipt of the last questionnaire. This time period is required for data collation, analysis and write up. In cases of early termination of the trial or temporary halt, the coordinating centre will notify the main REC within 15 days of the decision and detailed, written explanation for the termination/halt will be given.

10. Statistical considerations

10.1. Sample size

No formal sample size calculation has been undertaken for part 1 as our aim is to survey a large representative sample of women with LS, including those who have experienced RRH.

Given that the UK population is approximately 67,000,000 (67), the prevalence of LS is estimated as 1 in 280-370 (9, 10), and that an estimated 95% of individuals with pathogenic variants are unaware of this; there are therefore an estimated 9,054-11,964 people in the UK who are aware that they have LS, or 4527 - 5982 women. The proportion of women with LS who have undergone RRH is approximately 30% (68); an estimated 1358 – 1794 UK women.

A desirable sample size would include 250 women *who have undergone RRH*, with a lower limit of 100, and an upper limit of 400. This allows for sufficient post-hoc exploratory analysis. This translates to an overall desirable sample size of respondents of 750 women with LS (regardless of RRH history), with a lower limit of 300, and an upper limit of 1200. This sample size is in line with previous questionnaire studies in women at inheritable risk of gynaecological cancers (62). The number of people approached would therefore be dependent on the response rate. Assuming a response rate of 35%, the number of participants invited can vary from 1392, 557, 2229 to achieve 750, 300 and 1200 respondents respectively.

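### Protocol section 10.1 puts the RRH share at about 30% but sizes the survey as if it were one third, so 750 and 300 respondents are expected to give about 225 and 90 women with RRH, not 250 and 100

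*Protocol*

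**What the plan says.** Everything at issue is in protocol section 10.1 (Sample size). It first estimates how many women in the UK know that they have Lynch syndrome (LS), 4527 to 5982, and applies an RRH share: "The proportion of women with LS who have undergone RRH is approximately 30% (68); an estimated 1358 – 1794 UK women".

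It then sets the aim in terms of women who have had RRH: 250, "with a lower limit of 100, and an upper limit of 400". The conversion to all respondents follows: "This translates to an overall desirable sample size of respondents of 750 women with LS (regardless of RRH history". The range placed around that total is stated in the same sentence: "with a lower limit of 300, and an upper limit of 1200".

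The totals are then carried into a mailing plan: "Assuming a response rate of 35%, the number of participants invited can vary from 1392, 557, 2229 to achieve 750, 300 and 1200 respondents respectively".

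The section also says how the numbers should be read: "No formal sample size calculation has been undertaken for part 1 as our aim is to survey a large representative sample of women with LS". No second RRH proportion appears in the protocol, and no plan to over-sample women with RRH is described. The inclusion criteria in section 8.1 do not select on RRH.

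**The concern.** One section uses two different values for the same quantity. The share behind the UK pool is 30%. The share behind the survey totals is one third. If 30% is right, the desirable total and the lower total are both expected to fall short of the RRH counts from which they were derived.

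The number of women with RRH matters for several reasons:
- The primary endpoint (section 6.3) is the utility score for RRH.
- Only women who have had RRH complete the second EQ-5D-5L, which refers to 4 months after surgery (section 7.4.1).
- A secondary objective (section 6.2) calls for separate pre- and postmenopausal scores, which divides this group further.
- The survey's utilities feed the Markov model (section 10.2).

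The most visible consequence is at the lower limit: a survey that just reaches its minimum of 300 respondents would be expected to miss its minimum of 100 women with RRH.

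**Working it through.** **Inputs, all from section 10.1.** RRH share about 30%. RRH targets 250 (desirable), 100 (lower), 400 (upper). Respondents 750, 300, 1200. UK women aware of LS 4527 to 5982. Response rate 35%.

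**Step 1: which share reproduces the UK pool?**
- At 0.30: 4527 × 0.30 = 1358.1 and 5982 × 0.30 = 1794.6. The protocol prints 1358 and 1794, so this step uses 0.30.
- At one third: 4527 / 3 = 1509 and 5982 / 3 = 1994. Neither matches.

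**Step 2: which share reproduces the survey totals?** Respondents needed = RRH target / share.

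| RRH target | Stated total | Implied share | Total at one third | Total at 0.30 |
|---|---|---|---|---|
| 250 (desirable) | 750 | 0.333 | 750 | 833.3, so 834 |
| 100 (lower) | 300 | 0.333 | 300 | 333.3, so 334 |
| 400 (upper) | 1200 | 0.333 | 1200 | 1333.3, so 1334 |

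One third fits all three pairs exactly and 0.30 fits none. The totals at 0.30 are about 11% larger (1 / 0.90 = 1.11).

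**Step 3: what do the stated totals yield at 0.30?**
- 750 × 0.30 = 225, which is 25 below 250 (10%).
- 300 × 0.30 = 90, which is 10 below 100 (10%).
- 1200 × 0.30 = 360, against a stated 400.

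If each respondent independently has a 0.30 chance of having had RRH, the exact binomial probability of at least 250 among 750 is 2.6%, and of at least 100 among 300 it is 11.6%.

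**Step 4: what does this do to precision?** The standard error of a mean utility scales with 1/√n. √(250 / 225) = 1.054, so a confidence interval from 225 women is about 5% wider than one from 250. The ratio at the lower limit is the same, √(100 / 90) = 1.054.

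**Step 5: invitations at a 35% response rate.** Invitations = respondents / 0.35.
- Corrected totals: 834 / 0.35 gives 2383; 334 / 0.35 gives 955; 1334 / 0.35 gives 3812.
- Stated totals: 750 / 0.35 gives 2143; 300 / 0.35 gives 858; 1200 / 0.35 gives 3429.

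The printed 1392, 557 and 2229 match neither set. That is a separate arithmetic error. It matters here only because the mailing figures have to be recalculated in any case.

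**The case against.** The strongest reply is that these are round planning numbers for a survey with no formal sample size calculation. The 30% is labelled approximate and describes women with LS in general. Respondents come from clinics, registries, research cohorts and charities (section 7.1), and women with prior endometrial, ovarian or cervical cancer are excluded (section 8.2), so their RRH share could differ by a few points in either direction. The RRH counts are justified as leaving room for exploratory analysis, not by a power or precision target, so 90 against 100 crosses no derived threshold.

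Most of that stands, and it limits the size of the point. It does not remove the contradiction. The protocol applied 0.30 exactly when it sized the UK pool, describes the intended sample as representative, and gives no reason for a higher share among respondents.

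Three stronger readings are tempting, and the protocol does not support them:
- A reader might infer that recruitment stops at 750 or 300 and so fails to deliver. Section 10.1 sets no such stop. It gives a range of 300 to 1200, and both 334 and 834 lie inside it, so 100 and 250 women with RRH remain reachable.
- A reader might count 360 against 400 as a missed target. The protocol calls 400 an upper limit, and falling short of a ceiling is not a failure.
- A reader might chain this with the mailing figures: 1392 × 0.35 = 487 respondents, × 0.30 = 146 women with RRH, 42% below 250. Most of that gap comes from the separate invitation error. This point contributes only the factor 0.30 / 0.333 = 0.90.

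**Conclusion.** The point holds as an internal inconsistency with a modest consequence. At the protocol's own 30%, the desirable and lower totals are each expected to fall 10% short of the RRH counts they are said to deliver, and the stated minimum survey size does not match the stated minimum number of women with RRH. The upper pair is inconsistent in the same way, but only as a label on a ceiling.

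This rests on two things. The first is that 30% applies to respondents, which is the only value the protocol offers. The second is that the factor of 3 stands for an assumed share of one third. The protocol does not write that share down, but it fits all three pairs exactly. The shortfall is one of expectation, not certainty, and no power or precision claim is broken by it.

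**What to change.** Make section 10.1 use one proportion throughout. Either of these would do:
- Restate the totals as 834 respondents (lower 334, upper 1334) for 250, 100 and 400 women with RRH.
- Keep 750, 300 and 1200, and state the expected numbers with RRH as 225, 90 and 360.

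If the sponsor does expect about one third of respondents to have had RRH, the protocol should say so and give the reason.

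Then recalculate the invitations from the totals that are kept: 2383, 955 and 3812 under the first option, or 2143, 858 and 3429 under the second, both at a 35% response rate.

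Tracking recruitment by the number of questionnaires received from women with RRH would be a useful optional aid, but the correction does not require it.

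The cost is a text change. The first option plans for about 11% more respondents. The second accepts a stated RRH yield 10% lower.

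### The invitation numbers in Section 10.1 (1392, 557, 2229) are the expected non-responders at a 35% response rate; the numbers to invite are 2143, 858 and 3429.

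*Protocol*

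**What the plan says.** All the relevant figures are in protocol Section 10.1 (Sample size), which concerns Part 1 only.

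- There is no power calculation: "No formal sample size calculation has been undertaken for part 1".
- The target is set in women who have had RRH: "A desirable sample size would include 250 women", "with a lower limit of 100, and an upper limit of 400". The section converts this to 750 respondents overall, with limits of 300 and 1200.
- On uptake of surgery: "The proportion of women with LS who have undergone RRH is approximately 30" per cent.
- The section says that how many people are approached will depend on the response rate. It then gives the invitation numbers: "Assuming a response rate of 35%, the number of participants invited can vary from 1392, 557, 2229 to achieve 750, 300 and 1200 respondents".
- It estimates that 4527–5982 women in the UK know that they have Lynch syndrome.

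No other section gives a different response rate or a different number to invite.

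**The concern.** The sentence takes a response rate and a number of respondents and reports a number to invite. At 35%, roughly three women must be invited for each reply, yet 1392 is less than twice 750. The three figures therefore cannot follow from the stated rate.

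The primary endpoint (Section 6.3) is the utility score for RRH, and those scores feed the economic model in Section 10.2. With no formal calculation, the RRH targets are the only stated guard on how much information Part 1 will yield, and this sentence turns them into an invitation plan. If the mailing is planned and costed from it, the response will be well below what the protocol expects even when the 35% assumption is exactly right. The sentence also makes the study look easier to recruit to than it is.

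**Working it through.** **Inputs (all from Section 10.1).** Response rate 0.35; respondents N = 750 (desirable), 300 (lower limit), 1200 (upper limit); stated invitations 1392, 557, 2229; RRH targets 250, 100, 400; RRH share 30% as stated, or one third as implied by 250/750; pool 4527–5982 women.

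**1. Reproducing the stated figures.** Expected non-responders = (N/0.35) × 0.65:

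- 750 × 0.65/0.35 = 1392.9 (stated 1392)
- 300 × 0.65/0.35 = 557.1 (stated 557)
- 1200 × 0.65/0.35 = 2228.6 (stated 2229)

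All three agree to within 1. Other plausible slips do not fit: N/0.65 gives 1154, 462, 1846; N × 1.35 gives 1013, 405, 1620; N × 1.65 gives 1238, 495, 1980.

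**2. Invitations needed.** N/0.35, rounded up:

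- 750/0.35 = 2142.9, so 2143
- 300/0.35 = 857.1, so 858
- 1200/0.35 = 3428.6, so 3429

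These are about 54% above the stated figures (2143/1392 = 1.54).

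**3. Yield of the stated invitations at 35%.**

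- 1392 × 0.35 = 487 respondents, 263 short of 750
- 557 × 0.35 = 195, 105 short of 300
- 2229 × 0.35 = 780, 420 short of 1200

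Each shortfall is 35%. This follows from the error itself, because 0.35 × (0.65N/0.35) = 0.65N.

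**4. Response rate at which the stated invitations would suffice.** 750/1392 = 53.9%; 300/557 = 53.9%; 1200/2229 = 53.8%.

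**5. Women with RRH among those respondents.**

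| Invited | At 30% | At one third | Protocol figure |
|---|---|---|---|
| 1392 | 146 | 162 | 250 (desirable) |
| 557 | 58 | 65 | 100 (lower limit) |
| 2229 | 234 | 260 | 400 (upper limit) |

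**6. Share of the pool.** Desirable: 2143/5982 = 36% to 2143/4527 = 47%. Upper limit: 3429/5982 = 57% to 3429/4527 = 76%. The stated 2229 would have been 37% to 49%.

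**The case against.** The strongest reply is that little depends on this number. The protocol disclaims a formal calculation, and its synopsis (Section 4) lists the number of participants as not applicable. Section 10.1 makes the number approached depend on the response rate, and nothing caps it. Section 7.1 also recruits through charity websites, mailing lists and the study website, where no site invitation is needed. Section 15 provides for regular monitoring of recruitment and Section 16 for monthly coordinating-centre meetings, so a low response could be seen and more invitations sent. All of this stands. It limits the consequence but does not make the printed figures right, because the sentence states a number for a stated rate.

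Three stronger readings are tempting and are not supported:

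- A reader might infer that this is the only figure that sizes recruitment. It is not: the targets of 250 women with RRH and 750 respondents do that, and the invitation count is derived from them.
- A reader might infer that even the upper-limit mailing would miss 250 women with RRH. That holds at a 30% share (234) but not at the protocol's own one-third conversion (260).
- A reader might infer that the study would fall outside its acceptable range. The desirable mailing would still give 146–162 women with RRH, within the stated limits of 100 and 400, and falling below an upper limit is not a missed target. Only the lower-limit mailing falls below the stated minimum.

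Nor can the loss be put as a loss of precision in the utility score, because the protocol gives no standard deviation.

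**Conclusion.** The figures are wrong as written. Section 10.1 labels expected non-responders as the number to invite, and the match on all three values leaves little doubt about how it arose. At the protocol's own 35%, the stated invitations fall 35% short of each respondent number. The lower-limit mailing would miss the minimum of 100 women with RRH, and the desirable mailing would miss 250, on either RRH share.

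The conclusion on the invitation numbers rests only on the protocol's response rate and respondent numbers. The RRH counts also rest on a share of 30% to one third among respondents. The yields count replies to invitations alone; respondents from the open routes would add to them by an amount that the protocol does not estimate. The effect is on the invitation plan and the stated feasibility. The endpoint, the analysis and the respondent targets are unaffected.

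**What to change.** In Section 10.1, replace 1392, 557 and 2229 with 2143, 858 and 3429, for 750, 300 and 1200 respondents at a 35% response rate. Add that the desirable figure is about 36–47%, and the upper-limit figure about 57–76%, of the estimated 4527–5982 women who know that they have Lynch syndrome, so that sites and the ethics committee can judge feasibility.

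The cost is a one-line correction and provision for more invitations: 751, 301 and 1200 more at the three levels (2143 − 1392, 858 − 557, 3429 − 2229). The restated numbers make recruitment look harder.

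A separate matter can be settled in the same edit. The respondent numbers use a one-third RRH share while the text states about 30%; at 30%, 250, 100 and 400 women with RRH would need about 833, 333 and 1333 respondents. If the share is changed, the invitation numbers and pool percentages must be recalculated, because those given here apply to 750, 300 and 1200 respondents only.

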10.2. Method of analysis

Baseline characteristics will be calculated using descriptive statistics. Appropriate statistical tests will be used. Chi-square tests will be used to compare categorical

variables and t-Test (parametric) and Mann-Whitney (non-parametric) tests to compare continuous outcome variables between two groups. Appropriate Logistic/ Linear regression models will be used to evaluate impact of covariates on Linear outcome variables. The data set will be subject to two analysis formats to minimise the risk of bias during interpretation. Initially by cohort-matching, to reduce the influence of confounding variables. Secondly by regression analysis to analyse the impact of covariates of the categorical and linear variables. All analysis will be performed on R (R Core Team, Foundation for Statistical Computing, Vienna, Austria), or equivalent software package.

A Markov model built in TreeAge software (TreeAge, Williamstown, MA) will form the basis of an economic evaluation on the cost-effectiveness of RRH for endometrial cancer risk threshold at which to perform surgical prevention (hysterectomy) or other non-surgical preventive interventions (such as the levonorgestrel-intrauterine system, or other chemo-prevention) for endometrial cancer risk. Models will be built in order to evaluate lifetime costs as well as effects with undertaking 'risk reducing hysterectomy' in premenopausal and postmenopausal women by comparing it with 'no risk reducing hysterectomy' at varying levels of endometrial cancer risk. Additional modelling will also evaluate lifetime costs as well as effects as well as effects of endometrial cancer risk. Additional modelling will also evaluate lifetime costs as well as effects of endometrial cancer risk. Additional modelling will also evaluate lifetime costs as well as effects of endometrial cancer risk. Additional modelling will also evaluate lifetime costs as well as effects with undertaking non-surgical preventive interventions in premenopausal and postmenopausal women by comparing it with 'no intervention' at varying levels of endometrial cancer risk. The analysis will be undertaken primarily within the UK National Health Service (NHS) context. We will also explore the impact of outcomes in other health systems.

Utility score data for the model will be obtained from this survey study. Additional model parameters will be obtained from the published literature. A lifetime time horizon will be used to capture all costs and benefits and the analysis will be conducted using a healthcare perspective. An appropriate discount rate will be applied to costs and outcomes. The ICER/QALY will be calculated, and compared with the NICE cost-effectiveness willingness-to-pay threshold to determine whether or not RRH±BSO is cost-effective and to determine the endometrial cancer risk thresholds for undertaking hysterectomy for prevention. To investigate the sensitivity of the results, both deterministic and probabilistic sensitivity analysis will be performed.

11. Ethics

The study will receive full ethical approval prior to commencing recruitment.

The Chief Investigator will ensure that the study is carried out in accordance with the ethical principles in the Research Governance Framework for Health and Social Care, Second Edition, 2005 and its subsequent amendments as applicable and applicable legal and regulatory requirements.

The Principal Investigator will ensure that the study is carried out in accordance with ethical principles in the Research Governance Framework for Health and Social care legislation as well as any amendments.

In addition to this, the research team have considered multiple ethical issues:

- 1. Participants may feel obliged to take part: When participants are approached in person, especially during a visit to outpatient clinic, they may feel obliged to take part in the study. To address this issue, we emphasise that participation is voluntary, participants do not have to respond and are given the opportunity to take the information away and respond at a later date. We emphasise that declining to take part in the study will have no impact on their future care.
- 2. Participant burden: Participants will be contacted by email or during their attendance at outpatient clinic and they may feel burdened. To address this, we emphasise that there is no obligation to complete the questionnaire. Participants can withdraw from the study at any point.
- 3. Increased anxiety for the participants: Our target population may already be facing a heightened period of anxiety and may need to consider making difficult decisions which can have a significant impact on their health and their family. Invitation to participate in our study may potentially add to anxiety in some individuals. In order to address this, all study participants will have the contact details for the research team who they will be able to contact for reassurance/to ask questions. Additionally, we make clear that participation is completely optional.
- 4. Internet-based tasks: Some participants will be approached by email. It is possible some may not be familiar with the online survey tool, and this could lead to anxiety and frustration in some. Women who are approached this way will already be engaging in an online support group and are more likely to be familiar with internet based tasks. Women are also offered the option of completing a postal questionnaire if they feel that this will be a more acceptable method for them, for part 1.
- 5. Obtaining consent from participants invited to take part by support groups/charities: Informed consent will be obtained from the participant after reading the information leaflet online and completing the web-based consent form. This does not allow opportunity for the participant to ask questions, when compared to obtaining informed consent in person. To address this, we have clearly highlighted contact details of the research team and independent charity organisations in the patient information sheet, should the participant wish to discuss concerns prior to giving consent. We have also built in a facility for the participant to save their responses on the web-based survey tool and return to it at a later date.
- 6. Breach of confidentiality: Any breach of confidentiality can cause distress and inconvenience to the participants. Great care will be taken to ensure that the data collected will be strictly confidential and not released to anyone else outside the study without the volunteer's consent. Questionnaire results will be entered on a secure password protected customised database held at the coordinating centre on a server at the Wolfson Institute of Population Health, Queen Mary University of London. This will be accessible only to members of the research team through a username/password protected computer. Each team member

will have a unique password and each computer a separate certificate key. The computers will not be accessible to unauthorised personnel. Paper copies (consent forms, questionnaire results) will be stored in a secure filing area in the coordinating centre. Unauthorised persons will not have access to this data. There is a special dedicated team of IT specialists to ensure and monitor data security. The IT team and environment is IG tool kit compliant.

